## 7. STUDY DESIGN

### 7.1. *Study population: Selection criteria*

#### **Inclusion Criteria**

1. All BCN Checkpoint and BCN PreP-Point clients.
2. 18 years and older.
3. HIV uninfected or diagnosed in the center in the last 7 days prior to the study inclusion.
4. Men that have sex with men or transgender women.
5. Signature of written consent form.
6. Ability to comply with the requirements of the study protocol.

#### **Exclusion Criteria**

1. Knowledge of HIV infection from more than 7 days
2. Knowledge of active HCV infection

### 7.2. *Study Schedule of Assessments*

This project will be performed in the BCN Checkpoint and BCN Prep-Point , which is a community center for sexual health care and detection of HIV and other STIs for MSM and TGW since 2006.

The services offered by both centers are focused on prevention through early/acute detection of HIV plus fast access to treatment, promotion of biomedical approaches, as well as the promotion of a healthy sexuality among the MSM community.

The center also has experience in systematic detection of asymptomatic STIs and their treatment to prevent their dissemination among the community and the general population. Fast linkage to care has been established in collaboration with "Fundació Lluita contra la Sida" and with the "Hospital Universitari Germans Trias i Pujol", wherein during 2019 a total of 7.581 persons were attended.

This study will have two different phases: phase 1 (first year) and phase 2 (second year).

All the participants should answer the "Sexual Behavior and demographics" questionnaire (Appendix 2), before any blood study extraction during phase 1 and phase 2.

#### **Phase 1:**

##### **1A. Assess the prevalence of untreated HCV infection among HIV-negative MSM and TGW.**

During the first year all clients of BCN Checkpoint (6,000-7,000) will be offered a serology test, Abbott rapid HCV test "SD BIOLINE HCV assay". It will take 5 minutes to obtain the test results.

If a positive result is obtained in serology test a Cepheid "Xpert® HCV VL Fingerstick" will be performed to identify HCV Viremic cases. The time to obtain the test result will be 60 min approximately.

In case of positive serology and positive viral load, Chemistry and Microbiology HUGTiP laboratories will be used for genotype study and hematology and chemistry.

In case of positive serology with negative viral load, standard lab serology will be also performed to confirm serology, thrown standard hospital lab circuit. If confirmation, this participant will be considered as previously HCV infection with spontaneous cure, if no treatment has been received previously (See table 1).

All participants diagnosticated with viremic HCV infection will be offered a 6 and 12 month post treatment visit to asses possible reinfections. Cepheid "Xpert® HCV VL Fingerstick" will be used as described before to evaluate reinfections. Theses visits will remain without changes during all phases of this study.

**1B.** Also, during the first year, 1.000 subjects with a previous negative "SD BIOLINE HCV assay" will be offered Cepheid "Xpert® HCV VL Fingerstick" tests to detect acute HCV infection if they fulfil at least one of the following criteriaxiii, xiv, xv, xvi, xvii, xviii, xix, xx, xxi, xxii, xxiii, xxiv:

1. Group sex with ChemSex use during last 3 months.
2. Slammering during last 3 months.
3. Fisting without gloves during last 3 months.
4. Sharing anal play toys without condoms during last 3 months.
5. Sharing sniffing roller for cocaine or other drugs during last 3 months.
6. Partner with active HCV or recently diagnosed with HCV on the last 3 months
7. PrEP use\*
8. Previous HCV Infection,
9. HIV infection recently diagnosticated.

*\*PrEP alone as unique criteria will not be considered condition to perform HCV viral load, if it is the only condition, as in our center PrEP users are screened before starting PrEP and each year with serologic screening. Also, HCV screening is performed in case of founding high liver enzymes levels in periodic blood tests performed in PrEP routine controls.*

The participants with a previous negative "SD BIOLINE HCV assay" and a positive "Xpert® HCV VL Fingerstick" will be confirmed with the Cepheid "Xpert® HCV Viral Load". In these cases, a standard lab serology, hematology and biochemical exam will be also performed thrown standard hospital lab circuit (See table 1).

**Table 1. Study Chronogram Phase 1**

	SCREENING	6 months Post Treatment visit*	12 months Post Treatment visit*
Informed consent	X		
Selection Criteria	X		
SD BIOLINE HCV assay	X		
Cepheid "Xpert® HCV VL Fingerstick"	a X	a X	a X
Xpert® HCV Viral Load	b X		
Routine Serology	c X		
genotype study/Hematology and biochemical analysis	d X		
Sexual behavior & demographics questionnaire	X		
PROMS questionnaire	X	X	X

- a) The participants that obtain a positive result from the SD Bioline HCV assay test will be confirmed with Cepheid "Xpert® HCV VL Fingerstick" to identify HCV viremic cases. Also first 1000 participants with a negative result from the SD Bioline HCV assay test that fulfills criteria mentioned on 1B point, will be confirmed with Cepheid "Xpert® HCV VL Fingerstick" to identify acute HCV infections. \*During V6MPTV and V12MPTM the fingerstick will be offered to all the participants with HCV infection detected during the screening visit.
- b) Acute infections with negative antibodies will be also tested with (Cepheid "Xpert® HCV Viral Load) to confirm viremic cases.
- c) In case of positive serology with negative viral load, standard lab serology will be performed to confirm serology, through standard hospital lab circuit.
- d) For the confirmed HCV Viremic cases, it will be analyzed the following parameters: blood count, Serum Creatinine, AST, ALT, GGT, alkaline phosphatases, direct and indirect Bilirubin, prothrombin time and the genotype study will be performed.

*\* Visits after 6 months and 12 months are optional and only are applicable for those patients that had been diagnosed and treated for HCV infection during the screening visit.*

After one year, a statistical analysis (interim analysis at 6 months\*) of the results will be made to determine associated factors for positive antibody test as well as for positive acute HCV test to set selection criteria for phase 2 of the study. A Draft of HCV pre-test Score will be developed with this first-year analysis and implemented during second phase.

\*Interim analysis will be used to evaluate data collection, correct incidences and to set up data analysis system. This will facilitate the results evaluation at the end of Phase 1 and it will allow to create the pre-test score to start the study Phase 2.

## Phase 2: Targeted testing

During the second year, selected criteria from pre-test score will be used to offer clients an HCV rapid antibody test "SD BIOLINE HCV assay". Estimation of tests: 2,000-3,000. Depending on the results obtained on the first year, this analysis could change.

In addition, about 300 participants that complies the SCORE criteria founded during phase 1 for acute HCV infection, will be performed Cepheid "Xpert® HCV VL Fingerstick". On Visits V6MPT and V12MPT, screening will be performed with Cepheid "Xpert® HCV VL Fingerstick".

The goal with both detection strategies is to uncover a 3-time higher prevalence rate, according to our experience with HIV criteria obtained after evaluation of factors.

Procedures in case of positive results will be as described on first year phase. Final report will focus on proposing how the model could be replicated in other similar cities and settings.

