### **1.10. Type of population and number subjects**

Men who have sex with other men or transgender women, that are HIV negative and comes to get tested in our center or are under controls in our center.

Estimated enrollment first Phase 6000-7000 participants. Second phase 2000-3000 participants.

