**Table 2. Study Chronogram Phase 2**

	SCREENING	6 months visit *	12 months visit*
Informed consent	X		
Selection Criteria **	X		
SD BIOLINE HCV assay	X		
Cepheid "Xpert® HCV VL Fingerstick"	X a	X a	X a
Xpert® HCV Viral Load	X b		
Serology	X c		
genotype study/Hematology and biochemical analysis	X d		
Sexual behavior & demographics questionnaire	X		
PROMS questionnaire	X	X	X

- a) About 300 participants that complies the SCORE criteria founded during phase 1 for acute HCV infection, will be performed Cepheid "Xpert® HCV VL Fingerstick". On Visits V6MPT and V12MPT, screening will be performed with Cepheid "Xpert® HCV VL Fingerstick".
- b) If the Xpert® HCV VL Fingerstick test is positive, and SD BIOLINE HCV assay is negative, a confirmation viral load test will be performed to the participant "Cepheid "Xpert® HCV Viral Load"
- c) In case of positive serology with negative viral load, standard lab serology will be performed to confirm serology, thrown standard hospital lab circuit.
- e) For the confirmed HCV Viremic cases, it will be analyzed the following parameters: blood count, Serum Creatinine, AST, ALT, GGT, alkaline phosphatases, direct and indirect Bilirubin, protrombine time and the genotype study will be performed.

\* Visits after 6 months and 12 months are optional and only are applicable for those patients that had been diagnosticated and treated for HCV infection during the screening visit.

\*\* The selection criteria will be defined according to the pre-test score founded during phase 1.

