### **7.3. Sample size predetermination**

This observational study will include up to 7000 participants during Phase 1 and up to 3000 participants during Phase 2. Size determination has been determined by expected users during the first year to participate in the cohort. It will not be possible to determine a necessary size to optimize this study as there are no data concerning HCV prevalence in HIV-uninfected MSM and TGW in our allocation.

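### Is the Phase 2 goal of a three-fold higher prevalence out of reach, given that no comparator or client pool is named?

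*Combined protocol and SAP*

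**What the plan says.** The goal stands in section 7.2 of the combined protocol and SAP, under Phase 2: "The goal with both detection strategies is to uncover a 3-time higher prevalence rate". Its only support is "according to our experience with HIV criteria obtained after evaluation of factors", with no reference prevalence and no account of how enrichment was measured for HIV.

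Section 1.10 gives the sizes: "Estimated enrollment first Phase 6000-7000 participants. Second phase 2000-3000 participants". Section 7.3 repeats the upper ends: "This observational study will include up to 7000 participants during Phase 1 and up to 3000 participants during Phase 2". It adds that no optimal size could be worked out because local prevalence data are lacking. The Phase 2 text marks its own number as provisional: "Estimation of tests: 2,000-3,000. Depending on the results obtained on the first year, this analysis could change". The second strategy is a viral load test in about 300 clients.

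Selection is left to the Phase 1 results. The text after Table 1 says the first-year analysis will look for "associated factors for positive antibody test as well as for positive acute HCV test to set selection criteria for phase 2", and the footnote to Table 2 says "The selection criteria will be defined according to the pre-test score founded during phase 1". In Phase 1, antibody-negative clients get a viral load test only if they meet a risk criterion; note a to Table 1 reads "Also first 1000 participants with a negative result from the SD Bioline HCV assay test" and then refers to those criteria.

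Neither the endpoints (section 8.2) nor the statistical analysis (section 9) mentions the three-fold figure.

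**The concern.** Three-fold is the only quantitative goal set for Phase 2, and the sentence leaves two things open: the reference prevalence, and the pool from which the tested clients are drawn. On a natural reading, the goal compares score-selected clients in Phase 2 with all clients tested in Phase 1. Testing a fraction n/N of a pool can raise prevalence by at most N/n, even if the score finds every positive. At the midpoints of the plan's ranges that limit is below 3, so the goal and the test numbers seem to conflict.

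If so, the study could be judged to have missed a goal it could never reach. Alternatively, the same score could be called a success or a failure according to a comparator chosen afterwards. The score is to be validated in Phase 2 (section 5.2) and the final report is to propose the model for other cities, so readers would care which comparison was meant.

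**Working it through.** **Inputs.** Phase 1 pool N = 6,000 to 7,000 (sections 1.10 and 7.2, Phase 1A). Phase 2 antibody tests n = 2,000 to 3,000 (sections 1.10 and 7.2, Phase 2). Seroprevalence 4.7% and 305 expected seropositives (section 11.5). Persons attended in 2019: 7,581 (section 7.2). Viral load tests: 1,000 in Phase 1B and about 300 in Phase 2.

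**The plan's own figure.** 0.047 × 6,500 = 305.5, which reproduces 305. The ends of the range give 0.047 × 6,000 = 282 and 0.047 × 7,000 = 329, so the plan worked from the midpoint.

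**Ceiling for the antibody strategy.** Let s be the share of all positives that the score captures. Prevalence among those tested divided by prevalence in the pool is s × N/n, with maximum N/n at s = 1. The share needed for three-fold is 3n/N. This assumes a Phase 2 pool of size N with the same underlying prevalence as Phase 1, and reads the goal as a ratio of 3.

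| N | n | Ceiling N/n | Share needed, 3n/N |
|---|---|---|---|
| 6,000 | 2,000 | 3.00 | 100% |
| 6,500 | 2,500 | 2.60 | 115% (not possible) |
| 7,000 | 3,000 | 2.33 | 129% (not possible) |
| 6,500 | 2,000 | 3.25 | 92% |
| 7,000 | 2,000 | 3.50 | 86% |
| 6,000 | 3,000 | 2.00 | 150% (not possible) |

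In counts at the midpoints, three-fold needs 3 × 0.047 × 2,500 = 352.5 seropositives against 305.5 in the pool. Three-fold is possible with at most N/3 tests: 2,000, 2,167 or 2,333 for N = 6,000, 6,500 or 7,000.

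**Dependence on the pool.** The plan does not say that the Phase 2 pool is the size of Phase 1. With 7,581 clients (an assumption; it is unclear which site that count covers), the ceiling is 7,581/2,500 = 3.03, and three-fold is possible up to 7,581/3 = 2,527 tests with a perfect score.

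**Dependence on the comparator.** Against clients below the cut-off, three-fold needs s = 3n/(N + 2n). At the midpoints this is 7,500/11,500 = 65%, which equals 0.652 × 2.60 = 1.70-fold against the overall figure. The N/n ceiling does not apply to this comparison.

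**Viral load strategy.** If 1,000 clients are eligible, as in Phase 1B (an assumption for Phase 2), the ceiling is 1,000/300 = 3.33, and three-fold needs 3 × 300/1,000 = 90% of the acute cases.

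**The case for a change.** The case for a change is that the gap is real and cheap to close. The sentence is complete as printed and names no comparator; no Phase 2 pool size is given; and nothing links the number tested to the goal. The ceiling does not depend on prevalence, so the lack of local data does not remove it. At the midpoint that the plan itself uses for its 305 cases, three-fold of overall Phase 1 seroprevalence cannot be reached. A 65% score could be reported as 3-fold or 1.7-fold.

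The gap and the arithmetic stand. The consequence is weaker. Clients below the cut-off are not offered the test in Phase 2, so the 3-fold reading could come only from Phase 1 data. With universal testing followed by targeted testing, Phase 1 seroprevalence is the comparator an analyst would use for the antibody strategy. For viral load, no overall Phase 1 figure exists among antibody-negative clients, and the Phase 1B risk-selected group is the only one available.

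The stronger remedies cost more than they give. Holding to three-fold at N = 6,500 would limit those flagged to N × s/3: 1,517, 1,733 or 1,950 clients at assumed sensitivities of 70%, 80% or 90%. All are below the planned minimum of 2,000 tests. At 80%, 0.2 × 305.5 = 61 seropositives would be left untested to achieve a ratio. Restating the target instead needs a pool size and a sensitivity that the documents do not give and that only Phase 1 can supply.

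**Conclusion.** No change to the plan is needed. The goal is under-defined, but the plan does not contradict itself: over its own ranges the ceiling is 2.00 to 3.50, so three-fold is attainable in part of that range with a highly sensitive score and unattainable in the rest. The 2.60 at the midpoints rests on a Phase 1-size pool, equal prevalence in both years, and overall Phase 1 seroprevalence as comparator; none of these is stated.

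The figure feeds no endpoint, test or sample size, so following the plan as written gives no wrong result. The design already leaves the cut-off and the number of tests open until Phase 1 data exist, which is when enrichment can be weighed against missed cases. What remains is a gap that analysts fill sensibly: give positives and numbers tested by phase and by test, and state the comparator beside any ratio.

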**Table 2. Study Chronogram Phase 2**

	SCREENING	6 months visit *	12 months visit*
Informed consent	X		
Selection Criteria **	X		
SD BIOLINE HCV assay	X		
Cepheid "Xpert® HCV VL Fingerstick"	X a	X a	X a
Xpert® HCV Viral Load	X b		
Serology	X c		
genotype study/Hematology and biochemical analysis	X d		
Sexual behavior & demographics questionnaire	X		
PROMS questionnaire	X	X	X

- a) About 300 participants that complies the SCORE criteria founded during phase 1 for acute HCV infection, will be performed Cepheid "Xpert® HCV VL Fingerstick". On Visits V6MPT and V12MPT, screening will be performed with Cepheid "Xpert® HCV VL Fingerstick".
- b) If the Xpert® HCV VL Fingerstick test is positive, and SD BIOLINE HCV assay is negative, a confirmation viral load test will be performed to the participant "Cepheid "Xpert® HCV Viral Load"
- c) In case of positive serology with negative viral load, standard lab serology will be performed to confirm serology, thrown standard hospital lab circuit.
- e) For the confirmed HCV Viremic cases, it will be analyzed the following parameters: blood count, Serum Creatinine, AST, ALT, GGT, alkaline phosphatases, direct and indirect Bilirubin, protrombine time and the genotype study will be performed.

\* Visits after 6 months and 12 months are optional and only are applicable for those patients that had been diagnosticated and treated for HCV infection during the screening visit.

\*\* The selection criteria will be defined according to the pre-test score founded during phase 1.

### **7.3. Sample size predetermination**

This observational study will include up to 7000 participants during Phase 1 and up to 3000 participants during Phase 2. Size determination has been determined by expected users during the first year to participate in the cohort. It will not be possible to determine a necessary size to optimize this study as there are no data concerning HCV prevalence in HIV-uninfected MSM and TGW in our allocation.

## 8. VARIABLES AND MEASURE INSTRUMENTS.

### 8.1. Study Variables

- Determination of acute HCV cases detected by viral load.
- Number of positive viremic results and cases per 100 person-years.
- HCV serologic prevalence.
- Number of positive serologic test with or without positive viremia.
- Time between confirmed diagnostic and start of treatment (Measured in days).
- Number of reinfections at 6 and 12 months after treatment.
- Identification of risk factors using the sexual behavior and demographics questionnaire
- Ratio of satisfaction using "Patient Reported Outcome Measures" (PROMs)
- Causes of treatment delay or loss to follow up
- Reinfections/treatments measured in percentage.

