#### Secondary End-points

- Characterization of risk factors associated with acute and chronic HCV infection in the MSM and TGW community to inform which individuals will benefit more from HCV screening.
- Evaluation of causes for treatment delay and/or loss to follow up a long the study
- Evaluation of reinfections after treatment during first year post treatment.
- Service user's punctuations achieved after experience in HCV testing.

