### **11.4. Risks and potential limitations**

As this project will be included in an ongoing project of community screening, recruitment is not expected to be a problem, however intensification of campaigns for promotion of HCV testing will be considered in case of lack of interest in our actual users.

Questions related to risk factors such as number of sexual contacts, drug use, etc. will be asked by the counselor and could produce an underestimation of these risk factors. However, we have been working with this kind of questionnaires for the last 15 years and users have never expressed any problem due to a peer-to-peer service, which allows a safe environment for the clients. All our staff and volunteers are previously selected and adequately trained.

Users with positive results could refuse to attend the medical specialist in the Hospital Germans Trias due to the distance. In this case derivation to other Hospital could be considered. However, treatment will last only 8-12 weeks and usually require no subsequent follow-up. So, in our opinion the interference of this problem in this study would be extremely limited, other Hospitals on the city are working in Test and Treat HCV strategy and referral has been done in the past; also, we will ask for follow up with the participant through telephone calls.

The Partner notification potential Contacts will be performed in our center in collaboration with the Public Health agency to offer testing to positive case contacts. However, in the MSM community this can sometimes be difficult or even not possible because users don't keep in contact with the most part of their sexual partners. From our center we are going to facilitate to get a test in all suspicious cases of contact to other cases.

Our team has been trained during years in the use of rapid tests, including HIV ELISA, PCR, and Syphilis rapid tests. In this cases HCV viral load could be performed at the same time, but also HCV serology could be sent to the lab, as BCN Checkpoint disposes of nurses and doctors at all opening hours (from 8.00 to 20.00 hours) to perform common blood test through standard venipuncture.

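### The reinfection percentage counts treated people who are never retested as not reinfected, and the plan has no case definition to separate reinfection from treatment failure

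*Combined protocol and SAP*

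**What the plan says.** Section 8.1 lists two reinfection variables: a count, "Number of reinfections at 6 and 12 months after treatment", and a ratio, "Reinfections/treatments measured in percentage". Section 8.2 makes this a secondary endpoint: "Evaluation of reinfections after treatment during first year post treatment".

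The data come from two visits. In section 7.2 (Phase 1, 1A), people found viraemic "will be offered a 6 and 12 month post treatment visit to asses possible reinfections", using the fingerstick viral load test. Note a to Table 1 says that "the fingerstick will be offered to all the participants with HCV infection detected during the screening visit". The footnote to Table 1 adds: "Visits after 6 months and 12 months are optional and only are applicable for those patients", meaning those diagnosed and treated. Table 2 carries the same footnote for Phase 2. Both tables mark no RNA test between screening and month 6, and mark genotype at screening only.

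Section 9 plans descriptive statistics for reinfections that it calls only possible. It gives no rule for people who are not retested. No section says what makes a positive result a reinfection.

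**The concern.** Two separate problems affect one percentage.

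The first follows from the written measure. The denominator is treatments, but the numerator can be observed only in people who accept an optional visit. Anyone not retested is in effect scored as free of reinfection. The plan expects some loss: its causes are a secondary objective (section 5.2) and a study variable (section 8.1).

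The second is a gap. Without a case definition, a viral load that is positive at the first attended visit may be a new infection or a treatment that did not clear the virus. Counting the latter would raise the percentage. A negative at month 6 followed by a positive at month 12 does not have this ambiguity.

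At stake is the interpretation of a named secondary endpoint. No test, sample size or primary endpoint depends on it.

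**Working it through.** **Inputs.** The measure is reinfections ÷ treatments (section 8.1). The expected number treated is 10-15 (section 5.2). Section 11.5 gives the same 10-15 for acute infections alone and says that the viraemic share of its 305 expected seropositives is unknown, so more people may be treated. The documents give no retest uptake, reinfection risk or failure rate; values for these below are assumptions. They also state no reinfection percentage to reproduce. The 305 does reproduce: 4.7% × 6,500 (midpoint of 6,000-7,000) = 305.5.

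**Step 1: weight of one person.**
- 10-15 treated: 1/10 = 10.0 points; 1/15 = 6.7 points.
- If 5% to 50% (assumed) of the 305 are viraemic and treated: 0.05 × 305 = 15.25, so 1/15.25 = 6.6 points; 0.50 × 305 = 152.5, so 1/152.5 = 0.7 points.

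**Step 2: denominator error alone.** Let *a* be the share retested and *r* the true first-year reinfection share of those treated, with retested people representative. The plan reports *a·r*, an error of −(1−*a*)·*r*. With *r* = 10%:
- *a* = 50%: 5.0% reported, error −5.0 points.
- *a* = 80%: 8.0% reported, error −2.0 points.

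This error is never upward.

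**Step 3: if failures are also counted.** Let *f* be the failure share of those treated. Suppose every positive is counted, and failures attend as often as reinfected people. The plan then reports *a*(*r*+*f*), an error of *a·f* − (1−*a*)·*r*. The sign changes at *f/r* = (1−*a*)/*a*:

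| Share retested *a* | Threshold for *f/r* |
|---|---|
| 90% | 0.11 |
| 80% | 0.25 |
| 67% | 0.50 |
| 50% | 1.0 |

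Example with *r* = 10% and *f* = 5%: at *a* = 50% the plan reports 0.50 × 15% = 7.5%, which is 2.5 points too low; at *a* = 90% it reports 0.90 × 15% = 13.5%, which is 3.5 points too high.

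**Step 4: illustration with assumed counts.** Fifteen people are treated. One is positive at month 6 with no earlier negative. Another is negative at month 6 and positive at month 12. If both are counted, the plan gives 2/15 = 13.3% (exact 95% CI 1.7-40.5), however many were retested.
- All 15 tested at both visits: the first-year range is 1/15 = 6.7% (0.2-31.9) to 2/15 = 13.3% (1.7-40.5). If the month 6 positive is a failure, the plan is 6.7 points too high; if a reinfection, it agrees.
- Ten tested at both visits: the first-year range is 1/10 = 10.0% (0.3-44.5) to 2/10 = 20.0% (2.5-55.6). If the month 6 positive is a failure, the plan is 3.3 points too high; if a reinfection, 6.7 points too low. The month 6 figures are 0/10 = 0% (0-30.8) to 1/10 = 10.0% (0.3-44.5).

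**The case against.** The strongest reply concerns the upward error. A reader might infer that the plan's own rule counts every first positive, so that two opposite errors are built in. The documents do not support that. Section 8.1 counts reinfections without saying that any first positive must be one. Section 6 allows the team to ask about treatment received and blood results from other public health units, which could supply a negative post-treatment RNA. The laboratory text in section 6 provides genotyping for a confirmed positive viral load without limiting it to screening, although the tables mark it only there. Nor is the remark in section 11.4 that "treatment will last only 8-12 weeks and usually require no subsequent follow-up" a testing schedule: it stands in a paragraph on distance to the hospital, which also promises telephone follow-up. So the upward error is possible, not prescribed. It remains possible because none of these sources is tied to a case definition.

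It can also be said that the counts at 6 and 12 months, together with the causes of loss to follow-up, would show much of the picture in so small a group. They would help, but they do not give the number retested.

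Finally, the differences in the illustration lie well inside the exact intervals. That is true and limits the importance of the point. It does not justify a denominator that includes people with no result.

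**Conclusion.** The point holds in two parts of unequal strength. The downward bias from dividing by treatments follows directly from the written measure and the optional visits; its size is (1−*a*)·*r* if retested people are representative. The possible upward error follows from a missing case definition and depends on how analysts use outside results and any later genotype. If first positives are counted without such a check, the net sign is unknown.

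The threshold in step 3 is not a general rule. It needs equal attendance by failures and reinfected people, one retest share for both visits, and every positive counted.

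One person is worth 6.7 to 10.0 points with 10-15 treated, or about 0.7 to 6.6 points under the assumed 5-50% of 305. The endpoint is descriptive and will be imprecise in any case. The correction is worth making because it removes an avoidable error cheaply; the primary results do not depend on it.

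**What to change.** In sections 8.1 and 9:

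1. Replace the denominator with treated people who have an RNA result, reported by visit: at month 6, those tested at month 6; at month 12, those tested at month 12 or already positive at month 6. Take the month 12 figure as the first-year result for section 8.2. A single pooled figure for anyone tested at least once would still count people seen only at month 6 as free of reinfection for the whole year.
2. State the numbers treated, retested and not retested at each visit.
3. Classify each positive as a reinfection (after a documented negative post-treatment RNA, including an outside result under section 6, or with a different genotype where available) or as recurrent viraemia of undetermined origin.
4. Report the percentage from the first class alone to both classes together, each end with an exact 95% CI.

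No visit or test is added. The costs are a smaller denominator, wider intervals and a range instead of one figure. Selective attendance is not corrected. In particular, month 6 positives stay in the month 12 denominator while month 6 negatives who do not return leave it, which can push that figure up when month 12 attendance is low. The counts by visit make this visible.

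A separate editorial matter: section 11.1 places the post-treatment visits in February 2023 to September 2024, but Phase 1 starts in June 2021. With the 8-12 weeks of treatment in section 11.4, someone treated at the start would reach month 6 around February to March 2022, before that window opens. The window and the Phase 1 visits in section 7.2 must be reconciled.
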